10.5.2 Safety Evaluation

For all safety analyses, the Safety population will be used. The assessment of safety will be based mainly on the frequency of AEs and on the number of laboratory values that fall outside of pre-determined ranges. Other safety data (i.e., ECG, vital signs) will be considered as appropriate.

For all safety analyses, the safety population will be used. The assessment of safety will be based mainly on the frequency of AEs and on the number of laboratory values that fall outside of pre-determined ranges. Other safety data (i.e., electrocardiogram, vital signs) will be considered as appropriate.

Adverse events will be summarized by presenting the number and percentage of patients having any AE, having an AE in each body system and having each individual AE. Any other information collected (e.g., CTC grades or relatedness to study drug) will be listed as appropriate. In addition, the incidence of pneumonitis AEs will be summarized by preferred term.

Deaths reportable as SAEs and non-fatal SAEs will be listed by patient and tabulated by the type of AE.

Laboratory data will be summarized by presenting shift tables using CTC grades (screening to most extreme post-screening value), by presenting summary statistics of raw data and change from baseline values (means, medians, standard deviations) and by the flagging of CTC grades in data listings.

Data from other tests (e.g., electrocardiogram or vital signs) will be listed and any other information collected will be listed as appropriate.

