8.3 Laboratory Tests

Each hematology, blood chemistry and serum lipid parameter will be summarized at the Baseline visit (Visit 1a), each cycle, the End of Treatment visit (last assessment up to and including 30 days after last dose date, including unscheduled assessments). The change from baseline will be presented at all post-baseline visits where this can be calculated.

Each coagulation parameter is collected at Screening Visit 1a and Day 1 of Cycle 2. These data will be listed.

Each urinalysis parameter will be collected at Screening Visit 1a and subsequently as clinically required. These data will be listed.

The hematology parameters collected are:

White blood cells (WBC), hemoglobin, hematocrit, platelets

Either: absolute neutrophils, absolute lymphocytes, absolute eosinophils, absolute basophils and absolute monocytes

Or: percentage neutrophils, percentage lymphocytes, percentage eosinophils, percentage basophils and percentage monocytes

The CRF allows for "other" differential counts to be recorded. These results will be listed only.

The blood chemistry parameters collected are:

Urea, blood urea nitrogen, creatinine, lactate dehydrogenase (LDH), total protein, fasting glucose, phosphorus, serum calcium, serum corrected calcium (calculated at baseline only), electrolytes (sodium, magnesium, chloride, and potassium), total bilirubin, gamma-glutamyl-transferase (GGT), albumin, alkaline phosphatase, alanine aminotransferase (ALT) (or SGPT), aspartate aminotransferase (AST) (or SGOT), uric acid

The serum lipid parameters collected are:

Total cholesterol, triglycerides, low-density lipoprotein (LDL), high-density lipoprotein (HDL)

The coagulation parameters collected are:

Prothrombin time (PT), International normalized ratio (INR)

All laboratory test results will be converted into Standard International (SI) Units by Data Management. Summary tables will present the results in SI Units.

The normal ranges for each parameter will also be included on the database so results can be calculated as being below, within or above the normal range.

Laboratory results will be graded using the Common Toxicity Criteria for Adverse Events (CTCAE) v3.0 document for each parameter where a CTC grade is defined. The parameters with grades defined are:

Hematology: WBC, hemoglobin, platelets and absolute neutrophils

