Blood Chemistry: Creatinine, fasting glucose, sodium, magnesium, potassium, albumin, bilirubin, GGT, SGOT (AST), SGPT (ALT) and alkaline phosphatase

Serum Lipid Profile: total cholesterol, triglycerides

A shift table will be presented showing the change from screening to most extreme post-screening value (including the End of Treatment visit and any unscheduled assessments) in CTC grading.

In the event that an unscheduled laboratory test is performed the data from this test will be listed. Unscheduled visit results will only be summarized if the unscheduled visit supersedes the scheduled visit's results. I.e. if a scheduled visit is missed, or the laboratory sample is not taken, or there are no results from the laboratory sample, but there is an unscheduled visit occurring prior to the next scheduled visit then the results from the unscheduled visit should be used instead.

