	Grade 4	xx (xx.x%)	xx (xx.x%)	xx (xx.x%)	xx (xx.x%)	xx (xx.x%)	xx
	Total	xx (xx.x%)	xx (xx.x%)	xx (xx.x%)	xx (xx.x%)	xx (100%)	xx
	Missing	xx	Xx	Xx	Xx	xx	xx
Parameter: Fasting Glucose (units)							
Most Extreme Post-Screening Visit 1a Value (N=xxxx)	Grade 0	xx (xx.x%)	xx (xx.x%)	xx (xx.x%)	xx (xx.x%)	xx (xx.x%)	xx
	Grade 1	xx (xx.x%)	xx (xx.x%)	xx (xx.x%)	xx (xx.x%)	xx (xx.x%)	xx
	Grade 2	xx (xx.x%)	xx (xx.x%)	xx (xx.x%)	xx (xx.x%)	xx (xx.x%)	xx
	Grade 3	xx (xx.x%)	xx (xx.x%)	xx (xx.x%)	xx (xx.x%)	xx (xx.x%)	xx
	Grade 4	xx (xx.x%)	xx (xx.x%)	xx (xx.x%)	xx (xx.x%)	xx (xx.x%)	xx
	Total	xx (xx.x%)	xx (xx.x%)	xx (xx.x%)	xx (xx.x%)	xx (100%)	xx
	Missing	xx	Xx	Xx	Xx	xx	xx
Etc.							

CTC grades are calculated from V3.0 of the CTCAE manual.
Percentages are based on the number of patients in the Safety Population with data at Screening and the visit of interest.

Source: Listing 16.3-2.1

Programming Note: Repeat for each blood chemistry parameter that has a CTC grade defined (see SAP text).

Table 14.3-4.1 (page 1 of n)
 Summary Statistics of Serum Lipid Profile by Visit
 Population Safety

Visit	Statistic						
	n	Missing	Mean	SD	Min	Median	Max
Parameter: Total Cholesterol (units)							
Baseline (N=xxxx)	xx	xx	xx.xx	xx.xxx	xx.x	xx.xx	xx.x
Cycle 1 Visit 2 (N=xxxx)	xx	xx	xx.xx	xx.xxx	xx.x	xx.xx	xx.x
Cycle 1 Visit 3 (N=xxxx)	xx	xx	xx.xx	xx.xxx	xx.x	xx.xx	xx.x
Cycle 2 Visit 4 (N=xxxx)	xx	xx	xx.xx	xx.xxx	xx.x	xx.xx	xx.x
Cycle 2 Visit 5 (N=xxxx)	xx	xx	xx.xx	xx.xxx	xx.x	xx.xx	xx.x
Cycle 3 Visit 6 (N=xxxx)	xx	xx	xx.xx	xx.xxx	xx.x	xx.xx	xx.x
Cycle 3 Visit 7 (N=xxxx)	xx	xx	xx.xx	xx.xxx	xx.x	xx.xx	xx.x
Cycle 4 Visit 8 (N=xxxx)	xx	xx	xx.xx	xx.xxx	xx.x	xx.xx	xx.x
Cycle 5 Visit 9 (N=xxxx)	xx	xx	xx.xx	xx.xxx	xx.x	xx.xx	xx.x
Cycle 6 Visit 10 (N=xxxx)	xx	xx	xx.xx	xx.xxx	xx.x	xx.xx	xx.x
Cycle 7 Visit 11 (N=xxxx)	xx	xx	xx.xx	xx.xxx	xx.x	xx.xx	xx.x
Etc.							

Source: Listing 16.3-3.1

Programming note: Table continues for remaining Cycles then presents and End of Treatment summary which will be the last on-treatment assessment. Repeat for each blood chemistry parameter in turn. Results should be shown in SI units.

Table 14.3-4.2 (page 1 of n)
 Summary Statistics of Change from Baseline in Serum Lipid Profile by Visit
 Population Safety

Visit	Statistic						
	n	Missing	Mean	SD	Min	Median	Max
Parameter: Total Cholesterol (units)							
Cycle 1 Visit 2 (N=xxxx)	xx	xx	xx.xx	xx.xxx	xx.x	xx.xx	xx.x
Cycle 1 Visit 3 (N=xxxx)	xx	xx	xx.xx	xx.xxx	xx.x	xx.xx	xx.x

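### The chemistry shift tables do not separate high from low grades, so the only tabulation by laboratory grade cannot report hyperglycemia as such

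*SAP*

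**What the plan says.** SAP 8.3 sets the grading standard: "Laboratory results will be graded using the Common Toxicity Criteria for Adverse Events (CTCAE) v3.0 document". The graded chemistry list names each analyte once: "Blood Chemistry: Creatinine, fasting glucose, sodium, magnesium, potassium, albumin, bilirubin, GGT, SGOT (AST), SGPT (ALT) and alkaline phosphatase". The summary rule follows: "A shift table will be presented showing the change from screening to most extreme post-screening value", expressed in CTC grades. Protocol 10.5.2 has the same rule, also without direction: "Laboratory data will be summarized by presenting shift tables using CTC grades (screening to most extreme post-screening value".

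The shell for Table 14.3-3.3 (SAP 11) shows one glucose panel, headed "Parameter: Fasting Glucose (units". Its post-screening rows run from Grade 0 to Grade 4 with no high or low label. The programming note applies that layout to the other analytes: "Repeat for each blood chemistry parameter that has a CTC grade defined (see SAP text".

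Elsewhere SAP 8.3 does recognise direction. It stores normal ranges so that "results can be calculated as being below, within or above the normal range". That status appears as an L or H flag in Listing 16.3-2.1 but is not used in the shift table.

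**The concern.** An unsigned grade is enough for an analyte that is toxic in one direction only. Where both a high and a low value can be graded, a Grade 3 cell could mean either of two opposite toxicities, and a single worst grade per patient has to choose between them by a rule that the SAP does not state.

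This matters most for glucose. Protocol 1.2.3.3 and 6.1.4.2 both report grade 3 hyperglycemia on RAD001. SAP 4.2.4 names laboratory values as one of two safety endpoints, alongside adverse events. In the SAP 11 list of outputs, the shift tables are the only ones that tabulate patients by laboratory grade.

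There is also a programming risk. For a two-way analyte, *most extreme value* could be coded as the highest value, the lowest value or the highest grade. SAP 9 calls for independent quality control, but the text gives the checker nothing to settle which is meant.

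**Working it through.** The plan gives no figure to reproduce here. The check applies the stated rule to the shell and counts what it can and cannot show.

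**Inputs**
- Graded chemistry parameters (SAP 8.3): creatinine, fasting glucose, sodium, magnesium, potassium, albumin, bilirubin, GGT, AST, ALT, alkaline phosphatase = 11.
- Rule (SAP 8.3, Protocol 10.5.2): screening grade against one most extreme post-screening grade.
- Layout (Table 14.3-3.3): one unsigned panel per parameter.
- Assumption: CTCAE v3.0 grades fasting glucose, sodium, potassium and magnesium in both directions. The documents cite the criteria but do not reproduce them. On this assumption 4 of 11 panels are affected.

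**Swings between screening and later**

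Give each graded value a sign: H1 to H4 for high, L1 to L4 for low. The table keeps only the number.
- Opposite-direction pairs: 2 starting directions × 4 screening grades × 4 later grades = 32.
- Equal grades, on the diagonal, read as no change: 2 × 4 = 8.
- Later grade higher, reads as worsening: 2 × 6 = 12.
- Later grade lower, reads as improvement: 2 × 6 = 12.
- Check: 8 + 12 + 12 = 32.

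Direction is missing in all 32. The counts enumerate cell types; the documents give no basis for how many patients would fall in them.

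**Illustrative records under the rule**

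| Record | Cell shown (screening to later) | What is hidden |
|---|---|---|
| Sodium L1 at screening, H1 later | 1 to 1 | A change of direction reads as no change |
| Potassium normal at screening, then L2 and H3 | 0 to 3 | The L2 is dropped; the 3 has no direction |
| Glucose normal at screening, one later grade 3 | 0 to 3 | Whether it is hyperglycemia or hypoglycemia |

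The third record involves no swing, so the ambiguity does not depend on an unusual patient.

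**Where direction survives**
- Listing 16.3-2.1 gives each result with its CTC grade and an L or H flag, patient by patient.
- Tables 14.3-3.1 and 14.3-3.2 give the minimum and maximum of values and of changes by visit. They show extremes but do not count patients by grade.
- Table 14.5-2.1 counts adverse events by preferred term, without grade. Under Protocol 7.6.1 an abnormal laboratory value is an adverse event only if it causes signs or symptoms, is clinically significant or needs therapy.

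None of these counts patients by grade and direction.

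**Screening columns**

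In the shell as it reads, the screening columns are Grades 1 to 4, Total and Missing, while the post-screening rows start at Grade 0. A patient at Grade 0 at screening, as in the second and third records, has no screening column. Splitting the panels by direction makes such patients more common, because anyone abnormal only in the other direction becomes Grade 0.

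**The case against.** The best counter-argument is that two-way grading of these four analytes comes from outside the documents. Classing results as below, within or above range applies to every parameter and concerns normal ranges, not CTC grades, so it cannot pick out four analytes. The documents themselves describe graded glucose toxicity only as hyperglycemia. This stands as a limit: the four analytes are an assumption to be checked against CTCAE v3.0. It does not remove the point. If only one direction were to be graded, the SAP would still have to say which.

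The study is also single-arm and descriptive, with no hypothesis test (SAP 7.6). No efficacy estimate changes, and the data to recover direction are already collected and listed. That is correct and limits the severity.

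Three stronger readings are tempting, and the documents do not support them:
- *Every swing from one direction to the other reads as no change.* This holds only for equal grades, 8 of 32 types. The other 24 appear off the diagonal, as worsening or improvement of unstated direction.
- *Any patient abnormal in both directions loses an event.* If one abnormality is at screening and the other later, both grades appear, one as column and one as row. A grade is dropped only when both directions occur after screening.
- *The direction of toxicity is lost from the report.* It is lost from the shift table. The listing keeps it in full, the by-visit summaries keep it in part, and a clinically relevant hyperglycemia recorded as an adverse event would be counted under its own term.

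Exclusion criterion 12 (Protocol 5.2) bars uncontrolled diabetes, defined as fasting glucose above 1.5 × ULN. This limits how high glucose can be at entry, and so which glucose swings can start from a high grade. It has no bearing on new high or low values during treatment.

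**Conclusion.** The point holds as a minor safety-reporting improvement. As written, the plan pools high and low abnormalities for each two-way analyte and leaves *most extreme* undefined by direction. The only tabulation by laboratory grade therefore cannot report hyperglycemia, a known effect of the drug, as such.

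The size is 4 of 11 chemistry panels, on the assumption that CTCAE v3.0 grades glucose, sodium, potassium and magnesium in both directions. How many patients would be affected cannot be estimated from the documents. PFS and the other efficacy analyses are untouched.

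**What to change.** In SAP 8.3, define *most extreme* as the worst CTC grade in a stated direction. In Table 14.3-3.3 and its programming note:

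1. Confirm against CTCAE v3.0 which listed parameters are graded in both directions. Fasting glucose, sodium, potassium and magnesium are expected.
2. Give each of these a high panel and a low panel. In each, cross-tabulate the screening grade in that direction against the worst post-screening grade in that direction.
3. Count a value abnormal only in the other direction as Grade 0 in that panel. A missing value stays missing.
4. Add a Grade 0 screening column, after checking the source shell in case the column was lost in conversion. The hematology and lipid shells (Tables 14.3-2.3 and 14.3-4.3) read the same way and should be checked together.
5. Keep the existing post-screening window. Starting the count at first dose would depart from both SAP 8.3 and Protocol 10.5.2, and the fix does not need it.

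The cost is about four extra panels (each of the four analytes goes from one panel to two), one extra column and a sentence in SAP 8.3. No new data are needed, because low or high status is already derivable from the stored normal ranges.

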8.4 Vital Signs

Body temperature, pulse rate, systolic and diastolic blood pressure will be collected at Screening Visit 1a, Baseline Visit 1b, day1 of each cycle and the End of Treatment visit. Height and weight will be collected at Screening Visit 1a only. The vital signs data, including any unscheduled assessments, will be listed.

8.5 Other Safety Assessments

The Karnofsky Performance Status will be assessed at Screening Visit 1a, Baseline Visit 1b, at day 1 of each subsequent cycle and at End of Treatment. The baseline data will be summarized as well as change from baseline for post-baseline visits. All data, including unscheduled assessments, will be listed.

Pulmonary function test (including spirometry, diffusion capacity of carbon monoxide and room air O₂ saturation at rest) will be performed at screening, as medically necessary if there is evidence of non-infectious pneumonitis, and at the end of the study. These data will be listed.

8.6 Dosage Administration and Compliance

Study medication, RAD001, is given as a 10mg oral dose to be taken daily until the end of treatment. The dose administered throughout the entire treatment period should be captured on the CRF, including any changes in dosing initiated by the investigator for patients unable to tolerate the planned dosage, and any changes as a result of lack of compliance with the planned dosing regimen by the patient.

The total duration of treatment will be calculated as the number of days from the first to the last dose of study medication inclusive (regardless of any breaks in treatment). The total duration of treatment will also be categorized as up to 4 months, >4 to 8 months, >8 to 12 months, >12 to 16 months, >16 to 20 months, >20 to 24 months and >24 months. This will be calculated by dividing the duration of treatment in days by 365.25/12. The duration in days will be summarized and the number of patients in each 4-month treatment category will also be presented.

All dosage administration data will also be listed.

9. PROGRAMMING/QC PLAN AND SOFTWARE/SYSTEM

All statistical programs will be written in SAS® 9.2 or higher. Programming will be done as per ██████████ Standard Operating Procedures and Work Instructions. All outputs produced will undergo an independent quality control (QC) and Senior Biostatistical Review (SBR). A QC and SBR Plan will be produced to detail the checks to be performed.

10. TECHNICAL PROGRAMMING SPECIFICATIONS

10.1 General notes

- All data listings should be sorted by country, investigator site, by patient, and by time point within patient, where appropriate.
- Table specific footnotes should be printed below the table, separated from the end of the table by one blank line and left aligned. Avoid numeric references, which can be confused with data; rather use asterisks and other non-numeric symbols to refer to footnotes. Patient-specific footnotes should be avoided.
- For tables that summarize categorical (discrete) data, an Unknown or Missing category should be added to any parameter for which information is not available for any patient. The table should make clear, whether the denominator for percentages includes the Missing category or not.
- Data in columns of a table should be formatted as follows:
 - alphanumeric values are left-justified
 - whole numbers (e.g., counts) are right-justified
 - numbers containing fractional portions are decimal aligned
 - All fractional numeric values should be printed with a zero to the left of the decimal point (e.g., 0.12, 0.3). If -0.0 value occurs due to rounding off it should be printed as 0.0.
 - Unless otherwise specified, percentage values should be printed with one digit to the right of the decimal point (e.g., 12.8%, 5.4%).
 - Less-than-signs “<0.1%” should be printed when values are >0.0 and <0.1%
 - If >100% occurs due to rounding off errors then present as 100%
 - Missing data should be represented as blank in listings, unless a missing category was explicitly defined.
 - Dates should be printed in SAS format DATE9. (e.g. 01Jul1994). Missing portions of dates should be represented on patient listings as dashes (e.g. --Jul1994).

10.2 Decimal places

Unless otherwise specified, the estimated mean and median for a set of values should be printed out to one more decimal place than the raw (observed) data and rounded appropriately. Standard errors (or standard deviations) should be printed out to two additional decimal places than the raw (observed) data and rounded appropriately.

Decimal places for summary tables and listings will be as follows:

- 3 decimal places (p-values; if p-value is less than 0.001, display <0.001).
- data precision + 2 decimal places (standard errors and standard deviations)
- data precision + 1 decimal place (means, medians)
- same as data precision (minimums, maximums)
- 1 decimal place (percentages)
- if percentage =100, no decimal is required.

For example, for age (with raw data in whole years):

N	xx
Mean	xx.x
S.D.	x.xx
Min	xx
Median	xx.x
Max	xx

10.3 Font size

Font size should be Courier 9 points. Line size is 120 characters. Page size is 30 lines per page.

Column headings should be in initial upper-case characters.

For numeric variables, include “unit” in column heading when appropriate.

11. TABLE AND LISTINGS SHELLS

Each table should be identified by a numeral, and the table designation (e.g., Table 1) should be centered above the title. A decimal system (x.y-c.d) should be used to identify tables and listings with related contents. Tables/listings should be internally paginated in relation to total length (i.e., page number should appear sequentially as page X of N, where N is the total number of pages within a table or listing). The title is in mixed-case characters. The title and table designation are single-spaced, but are separated from the table by at least a double space. The study population or subgroup (e.g., Intent-to-Treat Population) should be identified on the line immediately following the title.

Table 14.x-c.d (page n of y)
Title1
Title2
...
TitleN
Population / Subgroup

The tables are numbered starting from 14 (as per ICH guidelines), Figures start with 15 and Listings start with 16. Numbering then follows the pattern given below:

x takes the values 1 – Baseline (section 11.1)

- 2 – Visit (section 11.2)
- 3 – Lab (section 11.3)
- 4 – Conmed (section 11.4)
- 5 – AE/SAE
- 6 – Time-to-event analysis

c takes the values according to the topics under the respective section x.

d is the unique table number under a topic

Examples:

The first table under Patient Disposition will be numbered as: Table 14.1-1.1 and Listing 16.1-1.1. Table 14.2-5.3 refers to the third table under Patient Outcome topic in Visit section. See Sections 11.1 to 11.6 for full details of output grouping.

The output should contain information about the program name and the date when output was generated. This information should be given in a footnote (in the bottom row of a page) in the following format:

E:\EMD\EMR62202\abc.sas, (01Jun2003 10:15)

All output should have the four-line header (the 4th line is left blank) indicating the study protocol and the purpose of the analysis at the upper left margin:

Novartis
Protocol No.: CRAD001LIC01

Section 11.1– Demographic data

This section should include tables and listings for the following data:

1. Patient disposition
2. Demographic and other baseline characteristics (including medical history)
3. Diagnosis and extent of cancer
4. Prior antineoplastic therapy
5. Chest x-ray

Section 11.2– Visit data

This section should include tables and listings for the following data:

1. Vital signs
2. Karnofsky Performance status
3. Dose administration
4. ECG Assessments
5. Pulmonary Function Test

Section 11.3– Lab data

This section should include tables and listings for the following data:

1. Hematology
2. Blood Chemistry
3. Serum Lipid Parameters
4. Coagulation
5. Urinalysis

Section 11.4– Conmed and concomitant diseases data

This section should include tables and listings for the following data:

1. All concomitant medication

Section 11.5– AE/SAE data

This section should include tables and listings for the following data:

1. Summary of all adverse events
2. Adverse events by system organ class and preferred term

Section 11.6– Time-to-event data

This section should include tables and listings for the following data:

1. Summary of time to event data
2. Survival analysis

Table of contents for Table, Listing and Figures templates:

Outputs marked with an asterisk will only be produced if the Safety population differs from the ITT population.

Table Number	Title	Population
Table 14.1-1.1	Patient Disposition and Analysis Populations	
Table 14.1-1.2	Number (%) of Patients with Major Protocol Deviations Post Inclusion	ITT
Table 14.1-2.1	Patient Demographic Characteristics	ITT
Table 14.1-2.2*	Patient Demographic Characteristics	Safety
Table 14.1-2.3	Diagnosis and Extent of Cancer	ITT
Table 14.1-2.4*	Diagnosis and Extent of Cancer	Safety
Table 14.1-2.5	Medical History by System Organ class and Preferred Term	Safety
Table 14.1-2.6	Summary Statistics of Change from Baseline in Karnofsky Performance Status	Safety
Table 14.1-3.1	Summary of Prior Antineoplastic Therapy	ITT
Table 14.1-3.2*	Summary of Prior Antineoplastic Therapy	Safety
Table 14.1-3.3	Duration of Prior Antineoplastic Therapy (months)	ITT
Table 14.1-3.4*	Duration of Prior Antineoplastic Therapy (months)	Safety
Table 14.1-5.1	Summary of Chest X-ray Evaluation at Screening	Safety
Table 14.2-3.1	Summary of Duration of Treatment with Study Medication	Safety
Table 14.3-1.1	Normal ranges for Hematology and Blood Chemistry Parameters	
Table 14.3-2.1	Summary Statistics of Hematology by Visit	Safety
Table 14.3-2.2	Summary Statistics of Change from Baseline in Hematology by Visit	Safety
Table 14.3-2.3	Shift Table for CTC Grade for Hematology Parameters	Safety
Table 14.3-3.1	Summary Statistics of Blood Chemistry by Visit	Safety
Table 14.3-3.2	Summary Statistics of Change from Baseline in Blood Chemistry by Visit	Safety
Table 14.3-3.3	Shift Table for CTC Grade for Blood Chemistry Parameters	Safety
Table 14.3-4.1	Summary Statistics of Serum Lipid Profile by Visit	Safety
Table 14.3-4.2	Summary Statistics of Change from	Safety

	Baseline in Serum Lipid Profile by Visit	
Table 14.3-4.3	Shift Table for CTC Grade for Serum Lipid Profile Parameters	Safety
Table 14.4-1.1	Concomitant Medications and Non-Drug Therapies by ATC class and Preferred Term	Safety
Table 14.5-1.1	Summary of Adverse Events	Safety
Table 14.5-2.1	Treatment Emergent Adverse Events by System Organ Class and Preferred Term	Safety
Table 14.5-2.2	Deaths Reportable as Serious Adverse Events by System Organ Class and Preferred Term	Safety
Table 14.5-2.3	Serious Adverse Events by System Organ Class and Preferred Term	Safety
Table 14.6-1.1	Summary of Survival and End of Study Status	ITT
Table 14.6-2.1	Analysis of Progression Free Survival Rate	ITT
Table 14.6-2.2	Analysis of Progression Free Survival Rate – Sensitivity Analysis	ITT
Table 14.6-2.3	Progression Free Survival Descriptive Statistics	ITT
Table 14.6-2.4	Progression Free Survival Descriptive Statistics – Sensitivity Analysis	ITT
Table 14.6-2.5	Duration of Response Descriptive Statistics	ITT
Table 14.6-2.6	Objective Response Rate and Disease Control Rate	ITT
Table 14.6-2.7	Overall Survival Descriptive Statistics	ITT

Figure Number	Title	Population
Figure 15.6-2.1	Kaplan Meier Plot for Progression Free Survival	ITT
Figure 15.6-2.2	Kaplan Meier Plot for Progression Free Survival – Sensitivity Analysis 1	ITT
Figure 15.6-2.3	Kaplan Meier Plot for Progression Free Survival – Sensitivity Analysis 2	ITT
Figure 15.6-2.4	Kaplan Meier Plot for Duration of Response	ITT
Figure 15.6-2.5	Kaplan Meier Plot for Overall Survival	ITT

Listing Number	Title	Population
Listing 16.1-1.1	End of Treatment Status	All Treated Patients
Listing 16.1-1.2	Analysis Populations and Strata	All Patients
Listing 16.1-1.3	Failed Inclusion/Exclusion Criteria and Major Protocol Deviations	All Patients
Listing 16.1-1.4	All Protocol Deviations	All Patients
Listing 16.1-2.1	Patient Demographic Characteristics	All Patients
Listing 16.1-2.2	Relevant Medical History/Current Medical Conditions	All Patients
Listing 16.1-3.1	Diagnosis and Extent of Cancer	All Patients
Listing 16.1-3.2	Diagnosis and Extent of Cancer – Lesions	All Patients
Listing 16.1-4.1	Prior Antineoplastic Therapy – Medication Details	All Patients
Listing 16.1-4.2	Prior Antineoplastic Therapy – Response	All Patients
Listing 16.1-5.1	Baseline Chest X-Ray Evaluation	All Patients
Listing 16.2-1.1	Vital Signs by Visit	All Treated Patients
Listing 16.2-2.1	Karnofsky Performance Status by Visit	All Treated Patients
Listing 16.2-3.1	Study Drug Administration	All Treated Patients
Listing 16.2-3.2	Dosage Administration Details	All Treated Patients
Listing 16.2-4.1	ECG Assessments	All Treated Patients
Listing 16.2-5.1	Pregnancy Test Results	All Patients
Listing 16.2-6.1	Pulmonary Function Test – Spirometry	All Patients
Listing 16.2-6.2	Pulmonary Function Test – Diffusion Capacity for Carbon Monoxide	All Patients
Listing 16.2-6.3	Pulmonary Function Test – Pulse Oximetry	All Patients
Listing 16.2-7.1	Post-Baseline Chest X-Ray Evaluation	All Patients
Listing 16.2-7.2	Imaging	All Patients
Listing 16.3-1.1	Hematology by Visit	All Treated Patients
Listing 16.3-2.1	Blood Chemistry by Visit	All Treated Patients
Listing 16.3-3.1	Serum Lipid Profile by Visit	All Treated Patients
Listing 16.3-4.1	Coagulation by Visit	All Treated Patients
Listing 16.3-5.1	Urinalysis Dipstick Analysis by Visit	All Treated Patients
Listing 16.3-5.2	Urinalysis Microscopic Analysis by Visit	All Treated Patients
Listing 16.4-1.1	Concomitant Medications and	All Treated Patients

	Non-Drug Therapies	
Listing 16.4-2.1	Antineoplastic Therapy Since Discontinuation of Study Drug	All Treated Patients
Listing 16.5-1.1	All Adverse Events	All Treated Patients
Listing 16.5-2.1	Deaths Reportable as SAEs	All Patients
Listing 16.5-2.2	Non-Fatal SAEs	All Patients
Listing 16.6-1.1	RECIST Solid Tumor Response Assessment – Target Lesions	All Treated Patients
Listing 16.6-1.2	RECIST Solid Tumor Response Assessment – Non-Target Lesions	All Treated Patients
Listing 16.6-1.3	RECIST Solid Tumor Response Assessment – Overall Response	All Treated Patients
Listing 16.6-1.4	Survival Status at End of Study	All Treated Patients
Listing 16.6-1.5	Progression and Survival Details	All Treated Patients
Listing 16.7-1.1	Comments Listing	All Patients

Table 14.1-1.1 (page 1 of 2)
Patient Disposition and Analysis Populations

Disposition Reason	Total n (%)
Enrolled	xx
Completed	xx (xx.x%)
Withdrawn	xx (xx.x%)
Primary reason for early discontinuation of treatment	
Adverse event(s)	xx (xx.x%)
Abnormal laboratory value(s)	xx (xx.x%)
Abnormal test procedure result(s)	xx (xx.x%)
Patient withdrew consent	xx (xx.x%)
Lost to follow-up	xx (xx.x%)
Administrative problems	xx (xx.x%)
Death	xx (xx.x%)
Death due to study indication	xx (xx.x%)
Death due to other reason	xx (xx.x%)
New cancer therapy	xx (xx.x%)
Disease progression	xx (xx.x%)
Protocol deviation	xx (xx.x%)

Percentages are based on the number enrolled in the study. Enrolled is defined as patients who gave informed consent.

Disposition is assessed at the cut off date for analysis therefore completed patients are those remaining on study treatment at this time.

Source: Listings 16.1-1.1 and 16.1-1.2

Programming Note: See Section 7.3 of text for definitions of enrolled, completed and withdrawn.

Table 14.1-1.1 (page 2 of 2)
 Patient Disposition and Analysis Populations

Disposition Reason	Total n (%)
Intent-to-treat population	xx (xx.x%)
Safety population	xx (xx.x%)
First-line Patients	xx (xx.x%)
Second-line Patients	xx (xx.x%)
Still present in study at each visit (safety population)	
Baseline Visit	xx
Cycle 1 Visit 2	xx
Cycle 1 Visit 3	xx
Cycle 2 Visit 4	xx
Cycle 2 Visit 5	xx
Cycle 3 Visit 6	xx
Cycle 3 Visit 7	xx
Cycle 4 Visit 8	xx
Cycle 5 Visit 9	xx
Cycle 6 Visit 10	xx
Cycle 7 Visit 11	xx
Cycle 8 Visit 12	xx
...repeat for all treatment cycles	xx
End of Treatment	xx

Percentages are based on the number enrolled in the study.
 A patient is defined as being in the population at a visit if they have data at that visit or a subsequent visit. The population at the End of Treatment visit will be anyone who had data for at least one on-treatment visit.
 Source: Listings 16.1-1.1 and 16.1-1.2

Table 14.1-1.2 (page 1 of n)
Number (%) of Patients with Major Protocol Deviations Post-Inclusion
Population ITT

Protocol Deviation Description	Total N=xxxx n (%)
XXXXXXXX	xx (xx.x%)
Xxxx xxxxx	xx (xx.x%)
XXXXXXXXXXXXXXXXXXXXXXXXXXXXXXXXXXXX	xx (xx.x%)
Etc.	

Percentages are based on the ITT population.
Source: Listing 16.1-1.3

Table 14.1-2.1 (page 1 of 3)
 Patient Demographic Characteristics
 Population ITT

Demographic variable	Total N=xxxx
Age (years)	
N	xx
Mean	xx.x
SD	xx.xx
Min	xx
Median	xx.x
Max	xx
Missing	xx
< 65 years	xx (xx.x%)
>= 65 years	xx (xx.x%)
Sex	
Male	xx (xx.x%)
Female	xx (xx.x%)
Race	
Caucasian	xx (xx.x%)
Black	xx (xx.x%)
Oriental	xx (xx.x%)
Native American	xx (xx.x%)
Pacific Islander	xx (xx.x%)
Other	xx (xx.x%)
Missing	xx
Ethnicity	
Hispanic/latino	xx (xx.x%)
Chinese	xx (xx.x%)
Indian (Indian subcontinent)	xx (xx.x%)
Japanese	xx (xx.x%)
Mixed ethnicity	xx (xx.x%)
Other	xx (xx.x%)
Missing	xx

Demography information is collected at the baseline visit (Visit 1).
 Percentages are based on the number of patients in the ITT population with non-missing data for that parameter.
 Source: Listing 16.1-2.1, 16.2-1.1 and 16.2-2.1

Table 14.1-2.1 (page 2 of 3)
Patient Demographic Characteristics
Population ITT

Demographic variable	Total N=xxxx
Height (cm)	
N	xx
Mean	xx.xx
SD	xx.xxx
Min	xx.x
Median	xx.xx
Max	xx.x
Missing	xx
Weight (kg)	
N	xx
Mean	xx.xx
SD	xx.xxx
Min	xx.x
Median	xx.xx
Max	xx.x
Missing	xx
BMI (kg/m ²)	
N	xx
Mean	xx.xx
SD	xx.xxx
Min	xx.x
Median	xx.xx
Max	xx.x
Missing	xx

Demography information is collected at the screening visit (Visit 1a).
Percentages are based on the number of patients in the ITT population with non-missing data for that parameter.
Source: Listing 16.1-2.1, 16.2-1.1 and 16.2-2.1

Programming Note: This table will be repeated for the Safety population if this differs from the ITT population (Table 14.1-2.2).

Table 14.1-2.1 (page 3 of 3)
Patient Demographic Characteristics
Population ITT

Demographic variable	Total N=xxxx
Karnofsky Performance Status	
100%	xx (xx.x%)
90%	xx (xx.x%)
80%	xx (xx.x%)
70%	xx (xx.x%)
60%	xx (xx.x%)
50%	xx (xx.x%)
40%	xx (xx.x%)
30%	xx (xx.x%)
20%	xx (xx.x%)
10%	xx (xx.x%)
Missing	xx

Demography information is collected at the screening visit (Visit 1a) for all patients. Percentages are based on the number of patients in the ITT population with non-missing data for that parameter.

Source: Listing 16.1-2.1, 16.2-1.1 and 16.2-2.1

Programming Note: This table will be repeated for the Safety population if this differs from the ITT population (Table 14.1-2.2).

Table 14.1-2.3 (page 1 of 2)
 Diagnosis and Extent of Cancer
 Population ITT

Diagnosis variable	Total N=xxxx
Primary Site of Cancer	
Site 1	xx (xx.x%)
Site 2	xx (xx.x%)
Site 3	xx (xx.x%)
...	xx (xx.x%)
Missing	xx
Details of Tumor Histology/Cytology	
Histology/Cytology 1	xx (xx.x%)
Histology/Cytology 2	xx (xx.x%)
Histology/Cytology 3	xx (xx.x%)
...	xx (xx.x%)
Missing	xx
Histologic Grade	
Well differentiated	xx (xx.x%)
Moderately differentiated	xx (xx.x%)
Poorly differentiated	xx (xx.x%)
Undifferentiated	xx (xx.x%)
Unknown	xx (xx.x%)
Missing	xx

Diagnosis and extent of cancer information is collected at the screening visit (Visit 1a). Percentages are based on the number of patients in the ITT population with non-missing data for that parameter.
 Source: Listing 16.1-3.1 and 16.1-3.2

Programming Note: This table will be repeated for the Safety population if this differs from the ITT population (Table 14.1-2.4).

Table 14.1-2.3 (page 2 of 2)
 Diagnosis and Extent of Cancer
 Population ITT

Diagnosis variable	Total N=xxxx
Stage at Initial Diagnosis	
Stage 0	xx (xx.x%)
Stage I	xx (xx.x%)
Stage Ia	xx (xx.x%)
...	xx (xx.x%)
Missing	xx
Dosing Phase	
Dose escalation phase	xx (xx.x%)
Dose expansion phase	xx (xx.x%)
Missing	xx
Any Target Lesions	
Yes	xx (xx.x%)
No	xx (xx.x%)
Missing	xx
Any Non-Target Lesions	
Yes	xx (xx.x%)
No	xx (xx.x%)
Missing	xx
Any Sites of Metastasis to be Reported	
Yes	xx (xx.x%)
No	xx (xx.x%)
Missing	xx

Diagnosis and extent of cancer information is collected at the screening visit (Visit 1a). Percentages are based on the number of patients in the ITT population with non-missing data for that parameter.
 Source: Listing 16.1-3.1 and 16.1-3.2

Programming Note: This table will be repeated for the Safety population if this differs from the ITT population (Table 14.1-2.4).

Table 14.1-2.5
 Medical History by System Organ Class and Preferred Term
 Population Safety

System Organ Class Preferred Term	Total N = xxxx n (%)
Any relevant medical history/current medical conditions?	
Yes	xx (xx.x%)
No	xx (xx.x%)
Any active problems?	
Yes	xx (xx.x%)
No	xx (xx.x%)
System Organ Class 1	xx (xx.x%)
Preferred Term 1	xx (xx.x%)
Preferred Term 2	xx (xx.x%)
Preferred Term 3	xx (xx.x%)
System Organ Class 2	xx (xx.x%)
Preferred Term 4	xx (xx.x%)
Preferred Term 5	xx (xx.x%)

Patients experiencing more than one medical history within a system organ class or within a system organ class and preferred term are only counted once.
 Percentages are based on the number of patients in the Safety population.
 Source: Listing 16.1-2.2

Table 14.1-2.6 (page 1 of n)
Summary Statistics of Change from Baseline in Karnofsky Performance Status
Population Safety

Visit	Statistic						
	n	Missing	Mean	SD	Min	Median	Max
Cycle 1 Visit 2 (N=xxxx)	xx	xx	xx.xx	xx.xxx	xx.x	xx.xx	xx.x
Cycle 1 Visit 3 (N=xxxx)	xx	xx	xx.xx	xx.xxx	xx.x	xx.xx	xx.x
Cycle 2 Visit 4 (N=xxxx)	xx	xx	xx.xx	xx.xxx	xx.x	xx.xx	xx.x
Cycle 2 Visit 5 (N=xxxx)	xx	xx	xx.xx	xx.xxx	xx.x	xx.xx	xx.x
Cycle 3 Visit 6 (N=xxxx)	xx	xx	xx.xx	xx.xxx	xx.x	xx.xx	xx.x
Cycle 3 Visit 7 (N=xxxx)	xx	xx	xx.xx	xx.xxx	xx.x	xx.xx	xx.x
Cycle 4 Visit 8 (N=xxxx)	xx	xx	xx.xx	xx.xxx	xx.x	xx.xx	xx.x
Cycle 5 Visit 9 (N=xxxx)	xx	xx	xx.xx	xx.xxx	xx.x	xx.xx	xx.x
Cycle 6 Visit 10 (N=xxxx)	xx	xx	xx.xx	xx.xxx	xx.x	xx.xx	xx.x
Cycle 7 Visit 11 (N=xxxx)	xx	xx	xx.xx	xx.xxx	xx.x	xx.xx	xx.x
Etc.							

Programming note: Table continues for remaining Cycles then presents and End of Treatment summary which will be the last on-treatment assessment.

Table 14.1-3.1 (page 1 of n)
 Summary of Prior Antineoplastic Therapy
 Population ITT

